5.5.7 Management of the Low Neck/Supraclavicular Region (Match versus No Match)

It is recognized that comprehensive head and neck irradiation incorporating IMRT can be done in several ways, any of which is permitted for this study. Patient-specific QA measurements are required for all IMRT treatments. When a field “match” technique is used for treating the lower neck, patient-specific measurements should include a verification of the dose coverage in the gap region for each patient.

1. Match: The upper cervical lymphatics and primary tumor bed are treated with IMRT. The lower cervical lymphatics and supraclavicular region are treated with a single AP (or occasionally APPA for larger patients with posterior neck at high risk) non-IMRT technique. The latter non-IMRT field(s) is matched to the upper neck IMRT fields. This technique requires comprehensive mid-line spinal cord blocking in the lower neck

fields. This technique also allows for a simultaneous blocking of portions of the larynx, hypopharynx, and cervical esophagus in the lower neck fields. Matching 2 IMRT plans is allowed.

2. No Match: The entire clinical target volume (CTV) [upper and lower neck and primary tumor bed] is irradiated with IMRT. There is no match line between upper and lower portions of the regions at risk. In this technique, limiting radiotherapy dose to organs at risk (OARs), e.g., the cervical esophagus, is entirely achieved by inverse treatment planning via IMRT algorithms.

5.5.8 Dose Prescription

Doses to PTVs

See Sections above for definitions of CTVs and PTVs and their prescribed doses. The goal is for 95% of the PTV70 to receive ≥ 2 Gy with a minimum dose (cold spot) of no less than 66.5 Gy. It is recognized that portions of the PTV70 close to the skin may receive significantly less than 66.5 Gy. This is acceptable as long as cold spots within PTV1 do not exist at a depth deeper than 8 mm beneath the skin.

For planning prioritization and priorities in dose coverage, in the final plan, PTV1 will be the highest priority target structure. PTV2 and PTV3, if applicable, will be ranked in the IMRT planning as lower priority than PTV1 although usually at a higher priority than normal structures other than spinal cord and brain stem.

Doses to Normal Structures

Spinal Cord: The PRVcord (as defined in Section 5.3.6.) should not exceed ≤ 50 Gy to any volume in excess of 0.03 cc (approximately 3 mm x 3 mm x 3 mm). In treatment planning, the spinal cord PRV should be given the highest priority.

Brainstem: The PRVbrainstem (as defined in Section 5.3.6.) should not exceed 52 Gy to any volume in excess of 0.03 cc (approximately 3 mm x 3 mm x 3 mm). In treatment planning, the PRVbrainstem should be given less priority than the PRVcord but more priority than the other critical structures listed below.

Lips: Reduce the dose as much as possible. The mean dose should be < 20 Gy. This may be exceeded in oral cavity cancers.

Oral Cavity: Reduce the dose as much as possible. The mean dose should be < 30 Gy for the non-involved oral cavity. Efforts should also be made to avoid hot spots (> 60 Gy) within the non-involved oral cavity.

Parotid Glands: In most cases, it will be easier to spare one parotid than the other. The treatment planning goal will be for this individual parotid gland to receive a mean dose of < 26 Gy.

Taking into account new data suggesting monotonous improvement in saliva as dose is reduced, without a threshold (Dijkema 2010), the objective will be to reduce the mean doses to both parotid glands as much as possible.

Contralateral submandibular gland: If contralateral level I is not a target, aim to reduce mean contralateral submandibular gland to < 39 Gy.

OARpharynx: Reduce the dose as much as possible. Some recommended (but not mandatory) treatment goals include: 1) No more than 33% of the OARpharynx exceeds 50

Gy; 2) Mean dose < 45 Gy; 3) No more than 15% of the OARpharynx exceeds 60 Gy. Cervical

Esophagus: Reduce the dose as much as possible. Some recommended (but not required) treatment goals include: Mean dose < 30 Gy.

Glottic and Supraglottic larynx (GSL): Reduce the dose as much as possible. The glottic larynx mean dose is recommended to be ≤ 20 Gy. If whole-neck IMRT is used, under-dosage of PTV2/PTV3 adjacent to the glottic larynx will be limited to $< 10\%$ receiving $< 95\%$ prescribed dose (this under-dosage is similar to that caused by the laryngeal block inserted in the split-field IMRT; Webster 2009).

Mandible: Reduce the dose as much as possible. Hot spots within the mandible should be avoided. It is recommended that maximum dose within the mandible be < 66 Gy, except in areas overlapping PTV.

Unspecified Tissue Outside the Targets: No more than 1cc of unspecified tissue outside the targets can receive 74 Gy or more.

5.5.9 Planning Priorities and Goals

1. Spinal Cord
2. Brainstem
3. PTV1
4. PTV2 (if applicable)
5. PTV3 (if applicable)
6. a. OARpharynx
b. Parotid gland contralateral to primary tumor site
7. a. GSL
b. Esophagus
8. a. Lips
b. Oral Cavity
9. a. Parotid gland ipsilateral to primary tumor site
b. Mandible
10. Unspecified tissue outside the targets

5.5.10 Critical Structures

Note: All required structures must be labeled as listed in the table below.

Table 8. Standard Nomenclature for Normal and Critical Structures

Standard Name	Description	Reference Dose
GTV	Primary tumor and involved nodes	70
CTV70	Primary tumor and involved nodes	70
PTV70	CTV to PTV expansion should be 5 mm minimal margin without IGRT; 3 mm minimal margin with Daily IGRT	70
CTV60	First Echelon nodal regions	60
PTV60	CTV to PTV expansion should be 5 mm minimal margin without IGRT; 3 mm minimal margin with Daily IGRT	60
CTV50	Lower risk nodal regions	50
PTV50	CTV to PTV expansion should be 5 mm minimal margin without IGRT+ mm minimal margin with Daily IGRT	50
CTV54	Lower risk nodal regions	54
PTV54	CTV to PTV expansion should be 5 mm minimal margin without IGRT; 3 mm minimal margin with Daily IGRT	54
SpinalCord	Spinal Cord	≤ 48
SpinalCord_05	Planning risk Volume of 5 mm	≤ 50
BrainStem	Brain Stem	≤ 50
BrainStem_03	Planning Risk Volume of 3 mm	≤ 52
Parotid	Mean doses to one Parotid	≤ 26
OralCavity (excluding PTV's)	Oral Cavity	Mean dose ≤ 32

Mandible (excluding PTV's)	Mandible	D0.03cc < 66
OARPharynx	Uninvolved posterior pharyngeal wall plus adjacent constrictor muscles; should not include PTVs	Mean dose ≤ 40
Esophagus_Up	Cervical Esophagus	Mean dose ≤ 30
Larynx	Glottic/Supraglottic Larynx	Mean dose ≤ 35
NonPTV_7000	Maximum dose (hot spot > 1cc outside the PTVs)	D1cc < 63

5.5.11 Image-Guided Radiotherapy

Daily image guidance of IMRT may be achieved using any one or more of the following techniques:

- Orthogonal kilovoltage (KV) images
- Linear-accelerator mounted kV and MV cone-beam CT images (CBCT)

5.5.12 Radiation Therapy Treatment Interruptions

Treatment interruptions are strongly discouraged. Treatment breaks must be clearly indicated in the treatment record when they occur. Patients who have treatment interruptions for >3 weeks will be taken off study. The interruption of radiation therapy for grade 4 mucositis / dermatitis / dysphagia is at the discretion of the treating radiation oncologist. Treatment breaks, if necessary, ideally should not exceed five treatment days at a time and ten treatment days total. Treatment breaks should be allowed only for resolution of severe acute toxicity and/or for intercurrent illness and not for social or logistical reasons. Cisplatin, pembrolizumab and ISA101b will not be administered during radiotherapy treatment breaks.

5.5.13 Radiation Therapy Adverse Events

The descriptions and grading scales found in the revised NCI Common Terminology Criteria for Adverse Events (CTCAE), version 5.0 will be utilized for grading all adverse events. All appropriate treatment areas should have access to a copy of the CTCAE, v. 5.0. A copy of the CTCAE, v. 5.0 can be downloaded from the CTEP web site (<http://ctep.cancer.gov>).

Grade 3 therapy-induced mucositis and/or dysphagia are expected to develop in about one third to one half of patients. Nutritional evaluation prior to the initiation of therapy for a prophylactic gastrostomy (PEG) tube placement is highly recommended. Placement of a feeding tube should be recorded on the appropriate case report form, as should use of a feeding tube during and after treatment (e.g., greater than or less than 50% of nutrition by tube). Other common radiation adverse events include: fatigue, weight loss, regional alopecia, loss of teeth or cavities, xerostomia, hoarseness, transient ear discomfort, dysgeusia, and skin erythema and desquamation within the treatment fields.

Less common long-term treatment adverse events include: hypothyroidism, loss of hearing, chronic swallowing dysfunction requiring permanent feeding tube, brachial plexopathy, and cervical fibrosis. Much less common radiation adverse events include: mandibular osteoradionecrosis (< 5% incidence with attention to dental recommendations), and cervical myelopathy (< 1% with restriction of spinal cord dose to ≤ 45 Gy).

5.6 Duration of Treatment and Follow-up

Complete treatment includes the course of definitive radiotherapy with concurrent chemotherapy and a total of 17 doses of pembrolizumab. In the absence of treatment delays due to adverse event(s), treatment may continue until disease progression or until one of the following criteria applies:

- Intercurrent illness that prevents further administration of treatment,
- Unacceptable adverse event(s),

- Patient decides to withdraw from the study, or
- General or specific changes in the patient's condition render the patient unacceptable for further treatment in the judgment of the investigator.

Patients will be administered pembrolizumab 200 mgs q 3 weeks starting week -1 for a total of 17 doses.

Patients will be followed for progression and survival using Standard of care intervals. Patients removed from study for unacceptable adverse event(s) will be followed until resolution or stabilization of the adverse event.

5.7 Participant Discontinuation Criteria

Discontinuation of study intervention does not represent withdrawal from the study.

As certain data on clinical events beyond study intervention discontinuation may be important to the study, they must be collected through the participant's last scheduled follow-up, even if the participant has discontinued study intervention. Therefore, all participants who discontinue study intervention prior to completion of the protocol-specified treatment period will still continue to be monitored in this study and participate in the study visits and procedures as specified in Section 2.2 unless the participant has withdrawn from the study.

Participants may discontinue study intervention at any time for any reason or be discontinued from the study intervention at the discretion of the investigator should any untoward effect occur. In addition, a participant may be discontinued from study intervention by the investigator or the Sponsor if study intervention is inappropriate, the study plan is violated, or for administrative and/or other safety reasons.

A participant must be discontinued from study treatment but continue to be monitored in the study for any of the following reasons:

- The participant or participant's legally acceptable representative requests to discontinue study intervention
- After prolonged study intervention interruption that prohibits restarting study intervention if agreed upon with the Sponsor
- Radiographic disease progression [outlined in Section 6.1.4](#).
- [Any progression or recurrence of malignancy, or any occurrence of another malignancy that requires active treatment](#)
- Any study intervention-related toxicity specified as a reason for permanent discontinuation as defined in the guidelines for dose modification due to AEs in Section 5.2.4.
- The participant has a medical condition or personal circumstance which, in the opinion of the investigator and/or sponsor, placed the participant at unnecessary risk from continued administration of study treatment.
- The participant has a confirmed positive serum pregnancy test

5.8 Dose Limiting Toxicity (DLT) Monitoring

Dose Limiting Toxicity will be continuously monitored and is explicitly intended for the purposes of safety monitoring of the concurrent combination of ISA101b, pembrolizumab and cisplatin-IMRT. As defined, excess DLT is not expected during standard of care cisplatin-IMRT. Excess DLT which delays SOC CRT greater than 2 weeks, however, would trigger protocol suspension and determination of causality attribution and whether the

protocol can proceed with all or only one of the investigational agent(s). Please see Section 10.3 for details of the Continuous Monitoring Plan.

5.8.1 DLT

DLT is defined as the occurrence of a severe adverse event (AE) listed below that is *at least possibly* related to ISA101b and pembrolizumab and occurs within 24 weeks of the initiation of ISA101b or pembrolizumab and leads to at least a two week delay in CRT. AEs will be graded according to NCI CTCAE version 5.0. The Data Safety and Monitoring Committee of the H&N Program at UPMC Hillman Cancer Center (HCC) will determine causality and whether to remove the suspension and permit the trial to proceed, in consultation with the Principal Investigator, key co-Investigator(s), ISA and Merck.

DLT Definition:

Since autoimmune/inflammatory events may occur at any time during the course of treatment, and may occur with evidence of clinical benefit, the following criteria will be used to define DLT:

- Any \geq Grade 3 non-hematologic toxicity **except**:
 - Grade 3 in-field radiation dermatitis for which IMRT is held \leq 1 week (5 fractions)
 - Grade 3 mucositis for which IMRT is held \leq 1 week (5 fractions)
 - Asymptomatic Grade 3 hypomagnesemia or hypokalemia, which corrects to Grade \leq 2 with replacement therapy
 - Grade 3 dysphagia
 - Grade 3 pain
 - Grade 3 weight loss
 - Grade 3 fatigue
- An alanine or aspartate amino transaminase elevation of greater than three times the upper limit of normal with concurrent elevation of bilirubin two times the upper limit of normal attributable to pembrolizumab should be considered a DLT. Patients meeting this criterion should be permanently discontinued from pembrolizumab.
- Autoimmune toxicity of any grade requiring systemic corticosteroids or other anti-inflammatory that cannot be tapered off in less than 12 weeks.
- Delay in completion of radiation therapy >10 fractions, or inability to complete prescribed IMRT course, due to immune toxicity at least possibly attributed to pembrolizumab or ISA101b.
- Grade \geq 3 neutropenia with fever (oral temperature $> 39^{\circ}\text{C}$)
- Grade \geq 3 thrombocytopenia with bleeding
- Grade \geq 3 local injection site reaction at the site of ISA101b injection
- Grade \geq 3 systemic allergic following ISA101b injection

Patients who experience a DLT to pembrolizumab will receive no additional doses of pembrolizumab and will be withdrawn from the protocol. Patients who experience a DLT to ISA101b will receive no additional doses of ISA101b but may continue on protocol treatment (cisplatin, IMRT, Pembrolizumab) with PI approval.

For any grade 5 event (death), the study will suspend if possibly related to the administration of investigational products. In such a case, a thorough assessment of the safety profile must be conducted, and the risk benefit consideration must be justified for any additional subject enrollment.

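### Sections 5.8, 5.8.1 and 10.3 do not state one delay event, and 5.8.1 leaves open which listed events are DLTs and what withdrawal means

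*Combined protocol and SAP*

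**What the plan says.** Section 5.8.1 describes a DLT twice. The lead sentence takes a listed severe event, at least possibly related to the investigational agents, that "occurs within 24 weeks of the initiation of ISA101b or pembrolizumab and leads to at least a two week delay in CRT". Under its DLT Definition heading it then says that "the following criteria will be used to define DLT" and gives eight criteria. One of them is a delay: "Delay in completion of radiation therapy >10 fractions, or inability to complete prescribed IMRT course". That item is limited to immune toxicity for which either agent may be responsible. Another is a liver finding: ALT or AST above three times the upper limit of normal (ULN) "with concurrent elevation of bilirubin two times the upper limit of normal attributable to pembrolizumab should be considered a DLT", followed by "Patients meeting this criterion should be permanently discontinued from pembrolizumab".

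Section 5.8 names the suspension trigger as "Excess DLT which delays SOC CRT greater than 2 weeks" and refers to 10.3 for details. Section 10.3 monitors delays of two weeks or longer in radiation plus cisplatin caused by ISA101b, pembrolizumab or both. It suspends the trial when the posterior probability that the delay rate exceeds 30% is above 50%.

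On consequences, 5.8.1 says: "Patients who experience a DLT to pembrolizumab will receive no additional doses of pembrolizumab and will be withdrawn from the protocol". Table 4 separately sets the action on pembrolizumab for each immune-related event and grade.

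**The concern.** Three things in this text do not fit together.

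- **The trigger.** Whether a patient delayed by exactly two weeks counts towards suspension depends on which section is read.
- **The DLT itself.** If the lead sentence governs, no event is a DLT unless it delays chemoradiotherapy (CRT) by two weeks. If the list governs, many events are DLTs with no delay at all, and each one attributed to pembrolizumab ends pembrolizumab. A site treating a listed event in the maintenance phase cannot tell from the text which applies.
- **The withdrawal instruction.** Read literally, it removes patients with pembrolizumab toxicity from the protocol. Two-year PFS is the primary endpoint, so censoring these patients at the toxicity would be selective rather than random.

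**Working it through.** **1. The 10.3 table reproduces.** The prior is Beta(1.5, 8.5). With x delays in n patients the posterior is Beta(1.5 + x, 8.5 + n − x), and the rule uses P(rate > .30). Evaluated at the upper n of each row, all 15 posterior values agree with the table to three decimals. The boundary arithmetic is sound; the question is which patients enter x.

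**2. The delay event, side by side.** Section 5.5.1 gives five fractions per week, so two weeks = 2 × 5 = 10 fractions.

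| Place | Threshold | Exactly 10 fractions counts? | Attribution |
|---|---|---|---|
| 5.8 | more than 2 weeks | no | not stated |
| 5.8.1 lead | at least 2 weeks | yes | ISA101b and pembrolizumab |
| 5.8.1 fraction item | more than 10 fractions | no | either agent |
| 10.3 | 2 weeks or more | yes | either or both |

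Ten treatment days is also the total that 5.5.12 says breaks should ideally not exceed, so it is not an arbitrary value.

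**3. Effect on the rule.** Take 4 patients, 3 of them delayed, one by exactly 10 fractions.

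- Counted as in 10.3: x = 3, posterior Beta(4.5, 9.5), P(rate > .30) = .541. Suspend.
- Counted as in 5.8: x = 2, posterior Beta(3.5, 10.5), P(rate > .30) = .305. Continue.

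One patient can matter in the same way elsewhere on the boundary: with 8 patients, 5 delays give .692 and 4 give .493. These cases are unlikely early on. At a fixed delay rate of 15% (the prior mean), 3 or more delays among 4 patients has probability 4 × .15³ × .85 + .15⁴ = .012.

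**4. Lead sentence against list.** Seven of the eight criteria have no two-week condition. Several parts of 5.8.1 fit a mandatory two-week CRT delay poorly:

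- The 24-week window runs from week −2 to about week 22. IMRT occupies weeks 0 to 6, so scheduled CRT ends about 9 weeks after the first vaccine. In the remaining 24 − 9 = 15 weeks an event cannot delay CRT given on schedule.
- Steroids started as early as week −2 cannot have failed a 12-week taper before week 10, after scheduled CRT.
- The dermatitis and mucositis exceptions turn on a hold of 5 fractions. A Grade 3 mucositis hold of 6 to 9 fractions falls outside the exception but does not meet the lead sentence.

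**5. Consequences for dosing.** Table 4 has 12 rows.

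- *Hypothyroidism, Grade 3–4.* Table 4 continues pembrolizumab. If the list governs, a related event ends it. This is the one direct clash, and it disappears if the lead sentence governs and CRT was not delayed.
- *Five further rows* (first Grade 3 colitis, diabetes/hyperglycemia, hypophysitis, hyperthyroidism, other Grade 3 events). Table 4 permits continuing or resuming at Grade 3 or above. Stopping satisfies both texts.
- *Liver.* ALT/AST above 3 to 5 times ULN with bilirubin 2 to 3 times ULN is Grade 2 in Table 4 (withhold, may resume). It is a permanent stop in 5.8.1 when attributable to pembrolizumab. Following the stricter rule breaches neither.

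**6. Follow-up.** Section 5.6 has patients followed for progression and survival. Section 5.7 says that stopping study intervention is not withdrawal from the study and keeps toxicity discontinuations under observation. Section 8.4 releases only patients with documented progression from scheduled assessments. Against this, 5.7 exempts anyone withdrawn from the study from further visits, and 5.6 follows patients removed from study for adverse events until the event resolves or stabilises.

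**The case against.** The strongest reply is that the text can be read coherently. The lead sentence speaks of events listed below it, so the list can be the catalogue and the delay the qualifier; this is grammatical and fits 5.8. Section 5.8 defers to 10.3, so the 10.3 threshold can be taken as operative. The joint attribution in the lead is loose wording, since 5.8.1 closes by treating a DLT to each agent separately. Most of this stands as a sensible reading. It does not make the wording consistent: 5.8 still states a different threshold for the same suspension, and the items in step 4 still sit badly with the delay requirement.

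A reader might infer three stronger things that the documents do not support.

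- *That 5.8.1 and Table 4 conflict across many rows, including the liver row.* Only hypothyroidism clashes directly, and only if the list governs. A figure such as 17 − 4 = 13 doses lost after a week-10 event rests on that reading alone; under the lead sentence the event is not a DLT once CRT has finished on schedule.
- *That a known number of patients lose PFS follow-up.* One could take 15% × 50 = 7.5 delayed patients, suppose half to all are pembrolizumab DLTs (3.75 to 7.5), and compare that with the accrual margin of 50 − 45 = 5. This uses a prior mean as a forecast, adds an assumed share and assumes the unfavourable meaning of withdrawal. Sections 5.6, 5.7 and 8.4 make treatment-only the more natural meaning, under which the loss is zero. Even if taken off study, such patients could still contribute person-time up to censoring in the exponential test.
- *That the 10.3 rule or its focus on CRT delay is wrong.* The table reproduces, and the focus is a stated choice.

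**Conclusion.** The concern holds as a defect of wording with limited but real consequences. The suspension trigger is contradictory at exactly two weeks, assuming two weeks equals 10 fractions; one such patient can decide between suspending and continuing, although the early scenario is improbable. The text does not settle whether a listed event without a two-week CRT delay is a DLT with a mandatory pembrolizumab stop. The withdrawal instruction most likely means off protocol treatment. Taken literally, however, it would censor the primary endpoint informatively in patients with pembrolizumab toxicity, and the number affected cannot be derived from the documents. The text should be corrected before sites have to act on it.

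**What to change.** 1. Use the 10.3 event in 5.8, in the 5.8.1 lead and in the fraction item: a CRT delay of two weeks or more (10 or more fractions) due to ISA101b and/or pembrolizumab. State that this event drives the 10.3 suspension rule.
2. State that a listed event is a DLT with the 5.8.1 consequence only when it causes that delay; that the 5.8.1 hepatic criterion is a permanent pembrolizumab stop regardless of delay; and that Tables 4 and 5 govern dosing after all other events.
3. Replace the withdrawal clause for a pembrolizumab DLT with discontinuation of pembrolizumab and continued follow-up for progression and survival as in 5.7 and 8.4. Naming 8.4 matters because the visit reference in 5.7 points to Section 2.2, which contains the secondary objectives.

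The cost is protocol wording in 5.8 and 5.8.1. The 10.3 boundary table, the sample size and the analysis stay as they are. There is one small downside: if the list was meant to govern, item 2 relaxes some mandatory stops (for example after a first Grade 3 colitis that did not delay CRT), so the clinical team should confirm it.
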